## Assessing the effect of nicotine reduction on ENDS users' addiction and exposure

### Background

The use of electronic nicotine delivery systems (ENDS) has reached epidemic levels among young people in the US. While estimates vary, ENDS have become the leading tobacco product used by young people in this country. ENDS heat and vaporize a nicotine-containing liquid to produce an inhalable aerosol mist. In addition to dependence-producing nicotine, ENDS emit other toxicants including aldehydes/carbonyls, a class of potent respiratory toxicants implicated in most non-cancer pulmonary diseases in cigarette smokers. Evidence indicates that young people using ENDS are likely to accelerate use, become nicotine dependent (ND), and initiate cigarette smoking. Epidemiological studies and market analysis moreover, suggests that "pod-mod" ENDS, JUUL in particular, had the biggest impact on the ENDS epidemic among young people. Unlike older ENDS generations, JUUL pioneered the use of nicotine salts which allowed to deliver high doses of nicotine in a smooth (protonated) form to users. Thus, addressing the addictiveness of ENDS through nicotine reduction (NR) can be a major regulatory strategy to reduce ENDS use among young people. In cigarette smokers, several observational studies and clinical trials have shown that smokers who switch to low nicotine cigarettes reduce daily nicotine intake, smoke fewer cigarettes, report lower dependence, and show higher trends in quitting. Similar patterns are expected in ENDS users, as our preliminary study of NR in young JUUL users shows that it leads to decreased satisfaction, dependence suppression, and intention to use in the future. However, reducing ENDS nicotine levels carries the risk of compensatory puffing and increased exposure. Evidence suggests that such compensation is dose and ND related, where very low nicotine products and beginning users are likely to have minimal compensation. Accordingly, assessing the potential role of NR regulations to reduce ENDS use and addiction requires standardized comparisons involving a range of NR levels and ENDS users at different stages of their use trajectory. It also requires assessing a wide array of outcomes to evaluate the effects of compensatory puffing on exposure to key pulmonary toxicants. These goals can be achieved by applying within-between subject comparisons to assess responses to a range of NR levels (partial vs. total) in ENDS users with different use profiles. Our team has pioneered the use of clinical and analytical lab methods to provide rapid and robust evidence about promising tobacco product manipulations for regulatory purposes (e.g. flavor). We plan to use these methods to compare among ENDS (e.g. JUUL) users the effect of 5% nicotine concentration, 3% (partial NR) or 0% (total or nicotine-free) NR on dependence, satisfaction, puffing behavior, clinical outcomes, and toxicant exposure. Our overarching hypothesis is that NR for ENDS will be associated with less satisfaction, withdrawal suppression, and intention to use and that such an effect will be more pronounced in total vs. partial NR. Our secondary hypothesis is that with very low nicotine ENDS and low dependence users, NR will cause minimal compensatory puffing and increased exposures. We will recruit current ENDS users (n=120; 21-35 yrs), for a 2X2 within- subject factorial crossover lab study. The nicotine conditions (5%, 3%) or (0%, 5%) x 2 time (pre-post) are the within-subject factors. A follow-up call at 3-months post-lab will be made to assess nicotine preference and changes in ENDS use.

We intend to answer 3 main regulatory questions that are directly responsive to this RFA's focus under Addiction; "Impact of changes in tobacco product characteristics (e.g. nicotine formulation) on dependence"; 1) is NR a promising regulatory option to reduce ENDS addictiveness and use; 2) what is the effect of partial vs. total NR on compensatory puffing and exposures; and 3) what is the effect of NR on ENDS users at different stages of use.

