## **Study Aims**

Aim 1. To assess the subjective and clinical effects of NR on ENDS users. Participants will undergo 2 ENDS use sessions that are preceded by 12-hour abstinence, with session order counter-balanced to mitigate order and carry-over effects. This study will focus on pre-post-use assessment of craving, withdrawal, satisfaction, intention to quit or use in the future, lung functions (e.g. FEV1 % predicted; FEV1/FVC, CO diffusing capacity-DLCO), and symptoms (e.g. dry mouth, eye irritation, palpitation, nausea). This aim will show ENDS users' response to NR on product satisfaction, dependence, lung functions and symptoms.

Aim 2. To assess puffing behavior in response to NR. Under the same protocol, puff topography (e.g. puff volume, puff frequency, duration) will be assessed continuously during the 2 sessions, while plasma nicotine will be measured pre-post sessions to assess nicotine boost and its correlation to puffing parameters. This aim will help understand users' compensatory puffing in response to NR and its effect on plasma nicotine.

Aim 3. To assess exposure to toxicants associated with NR. We will measure toxicant emissions (14 aldehydes) in the analytical lab using a smoking robot that reproduces the puff-by-puff behavior (playback) of each participant for all two nicotine conditions (Aims 1, 2). This aim will reveal how compensatory puffing behavior in response to NR influences acute exposure to pulmonary toxicants.

The proposed studies will give clear evidence on the potential of NR regulations to limit the addictiveness and use of ENDS, and to help predict any potential side effects of NR on ENDS users.

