## **AIM 1: To assess the subjective and clinical effects of nicotine reduction on ENDS users.**

Objective and hypothesis. This aim will help understand users' response to NR and how it will influence their product satisfaction, nicotine dependence, intention to quit or use in the future, lung functions, and clinical symptoms. We hypothesize that NR will be associated with less satisfaction, withdrawal suppression, and intention to use in the future and that such an effect will be more pronounced in total compared to partial NR and in high compared to low-frequency users.

Outcomes. We will utilize our clinical lab model to study the effect of NR on the following outcomes assessed according to the plan described in Table 2. All assessments will be based on instruments that are standard in clinical lab studies of addictive behaviors modified for the ENDS we plan to use (Vargas-Rivera et al., 2020). Participants will use a tablet to respond to these measures using RedCap.

**Outcomes.** We will utilize our clinical lab model to study the effect of NR on the following outcomes assessed according to the plan described in Table 2. All assessments will be based on instruments that are standard in clinical lab studies of addictive behaviors modified for the ENDS we plan to use (Vargas-Rivera et al., 2020). Participants will use a tablet to respond to these measures using RedCap. Briefly, we will assess;

1. Demographic and baseline characteristics; including age, race, sex, and reasons for ENDS use. Other characteristics will include the frequency of ENDS use, and the history of other tobacco/nicotine products use (Amato, Boyle & Levy, 2016; Zavala-Arciniega et al., 2019; Vargas-Rivera et al., 2020).
2. Dependence measures including; 1) *Use satisfaction* (Modified Cigarette Evaluation Questionnaire (mCEQ) (Arger et al., 2017); 2) *Dependence* (Questionnaire of Smoking Urges-brief and the Minnesota Nicotine Withdrawal Scale, Penn State Electronic Cigarette Dependence Index (Ben Taleb et al., 2018; Foulds et al., 2015; St Helen et al., 2017); 3) *Puff sensory effects* (Duke Sensory Scale, (Malson & Pickworth, 2002)).

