3. Use related measures including 1) *Harm perception* (Smith, Curbow & Stillman, 2007); 2) *Intention to quit or use in the future* (Wackowski et al., 2016); 3) *Reasons for ENDS use* (Kinouani, Pereira & Tzourio, 2017), and 4) Visual Analogue Scale (VAS) to measure ENDS use experience such as pleasantness, enjoyment, and pleasure from use (as in Vargas-Rivera et al., 2020).
4. Lung function tests (LFTs): LFTs (i.e., lung volume testing, airway resistance, specific airway conductance) will be measured before and immediately after ENDS use (Carlos et al., 2019). According to 2019 American Thoracic Society and European Respiratory Society recommendation (Graham, Jacobs & Amato, 2019) simple spirometry (e.g. FVC, % predicted value (pred), FEV1 % pred FEV1/FVC, % pred); forced expiratory flow (FEF) and Peak expiratory flow rate or PEFR) will be performed. Diffusing capacity for carbon monoxide (DLCO) will be determined using a rapidly resolving gas analyzer (RGA) (Neder et al., 2019) and the single-breath technique (Graham et al., 2017).
5. Clinical symptoms, such as (dry mouth, eye irritation, palpitations, and nausea) will be assessed pre-post ENDS use using standard clinical assessments (McConnell et al, 2017; Morice et al., 2007). Symptoms like cough, sore throat will be assessed after-session since our participants will be free of these symptoms pre-session to exclude potential COVID-19 cases (pls. see Inclusion and Exclusion criteria).
6. Cardiovascular measures: To monitor participants' vital signs, physiological measures will be monitored during each session such as heart rate, blood pressure, and pulse oximetry using the Noninvasive Patient Monitor 507E, Criticare Systems, Waukesha, WI.

7. Three-month follow-up call: Assesses Harm perception (Smith, Curbow & Stillman, 2007), *nicotine preference*, and *changes in ENDS and tobacco use* (Amato, Boyle & Levy, 2016; Zavala-Arciniega et al., 2019; Vargas-Rivera et al., 2020).

Table 2: Measures * Only during baseline	Measurement time			
	Pre	During	Post	3 month
Demographics*	X			
Tobacco use history	X			X
ENDS Use satisfaction (mCEQ subscale)			X	
Penn State Electronic Cigarette Dependence Index (10 items)	X			
Questionnaire of Smoking Urges (7-point Likert scale)	X		X	
Minnesota Nicotine Withdrawal Scale (score range from 0-100)	X		X	
ENDS Visual analog scale (0 not at all to 100 extremely)			X	
Duke Sensory Scale (7-point Likert scale)			X	
Peer and family influence	X			
Harm perception	X		X	X

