## **AIM 2: To assess the puffing behavior in response to nicotine reduction.**

**Objective and hypothesis.** This aim will help understand users' compensatory puffing behavior in response to NR and its effect on plasma nicotine as the main substance sustaining addiction to ENDS. *We hypothesize that NR-related compensatory puffing will be more pronounced in high vs. low-frequency users.*

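### The secondary hypothesis is about users with low dependence, but the plan gives its one graded dependence score no role in the analysis and uses frequency of use instead

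*Combined protocol and SAP*

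**What the plan says.** - **Hypothesis (Background).** The secondary hypothesis is that "with very low nicotine ENDS and low dependence users, NR will cause minimal compensatory puffing and increased exposures". The text shortly before it ties compensation to dose and to nicotine dependence, so dependence is the stated effect modifier.
- **Instruments (Aim 1, Outcomes).** Three are grouped under dependence: "Questionnaire of Smoking Urges-brief and the Minnesota Nicotine Withdrawal Scale, Penn State Electronic Cigarette Dependence Index".
- **Timing (Table 2).** The row "Penn State Electronic Cigarette Dependence Index (10 items" is marked in the Pre column only. The urges and withdrawal scales are marked both Pre and Post.
- **Aim 1 (Study Aims).** The pre-post focus is described as "This study will focus on pre-post-use assessment of craving, withdrawal, satisfaction, intention to quit or use in the future", and the section then promises: "This aim will show ENDS users' response to NR on product satisfaction, dependence, lung functions and symptoms".
- **User type elsewhere.** The Aim 2 hypothesis is that "NR-related compensatory puffing will be more pronounced in high vs. low-frequency users". The Aim 1 hypothesis, the randomisation within frequency groups (Experimental protocol) and the between-subject factor in Sample size also use frequency of use.
- **Statistical analysis.** The primary ANOVA has two within-subject factors, concentration and time. The mixed model adds personal attributes, with sex, education, race and SES given as examples. Sex is the only pre-planned interaction named. Aim 3 uses a one-way ANOVA and a regression of emissions on topography. The Penn State index is not mentioned.

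**The concern.** A hypothesis about how an effect varies with dependence needs a model in which the nicotine effect can vary with a measure of dependence. The plan collects such a measure and then leaves it out. The plan reaches the question only through frequency of use, which may track dependence well or poorly.

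At stake is the claim that compensation and added exposure are small in users with low dependence. If only a frequency comparison is run, a null result could mean that dependence does not matter, or that frequency is a weak stand-in for it. The report could not separate the two. This differs from the absence of a frequency term in the primary ANOVA: adding that term would serve the Aim 1 and Aim 2 hypotheses but would still leave the Background hypothesis tested by proxy.

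**Working it through.** **1. Plan's own figure.** Sample size gives 120 evaluable after at most 20% loss: 120 / (1 − 0.20) = 150, as stated. No figure in the plan concerns the Penn State score, so the finding rests on the text and the numbers below only size the remedy.

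**2. Where each item enters.**

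| Item | Hypothesis | Assignment / power | Named analysis |
|---|---|---|---|
| Dependence (Penn State score) | Background, secondary | none | none |
| Frequency of use | Aims 1 and 2 | both | not in the primary ANOVA |
| Urges, withdrawal (pre and post) | withdrawal in Aim 1 | none | condition × time ANOVA, as outcomes |

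The score could enter only through the open-ended covariate list, as a baseline difference adjusted for, or as an imputation predictor. None of these lets the nicotine effect differ by dependence.

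**3. What the missing test could detect.** Topography and playback emissions have one value per session. With two sessions, score × condition is therefore equivalent to regressing the within-person difference on the score. By Fisher's z, at two-sided 0.05 and 80% power, the detectable correlation is r = tanh[(1.960 + 0.842) / √(n − 3)].

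- n = 60 (reading 2X60 as 60 per product part): tanh(2.802 / √57) = tanh(0.371) = 0.355.
- n = 120 (pooled): tanh(2.802 / √117) = tanh(0.259) = 0.253.

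With the plan's correlation of 0.5, the SD of the difference is SD × √(2(1 − 0.5)) = 1 outcome SD. So r = 0.355 means that compensation shifts by 0.355 outcome SD per SD of score.

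**4. Illustration of the proxy's cost (all inputs assumed).** Let the score correlate 0.37 with the within-person difference at n = 60. Let frequency be a median split of a variable that correlates q with the score and acts only through it. A median split of a normal variable multiplies the correlation by √(2/π) = 0.798. Power is approximately Φ(atanh(r)·√57 − 1.96), plus a negligible lower tail.

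- Continuous score, r = 0.37: about 83%.
- Median split of the score itself, r = 0.37 × 0.798 = 0.295: about 63%.
- Frequency split, q = 0.3: r = 0.37 × 0.3 × 0.798 = 0.089, about 10%.
- q = 0.5: r = 0.148, about 20%.
- q = 0.7: r = 0.207, about 35%.

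Pooled at n = 120, the continuous score gives about 99% and the frequency split about 16%, 36% and 62%.

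**5. The same illustration reversed.** If frequency is the true moderator at 0.37 (n = 60), the frequency split has about 63%. The score, with r = 0.37q = 0.111, 0.185 and 0.259, has about 13%, 29% and 52%. The ranking depends on which variable is the true moderator, and the documents do not settle that.

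**The case against.** **Aim 1.** A reader might infer that, because the index is taken only before use, Aim 1 cannot show any dependence response. The documents do not support this. The protocol counts the urges and withdrawal scales as dependence measures, takes both before and after use, and describes Aim 1 as pre-post craving and withdrawal. They fit the condition × time analysis. Pre-only timing is also what a baseline moderator needs. What remains is a matter of wording: Aim 1 can show acute change in urges and withdrawal, not change in the index.

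**Frequency as the chosen measure.** The Background also speaks of beginning users and of different use profiles, and every aim-level statement uses frequency. Dependence as modifier appears only in the Background. Defining user type by frequency is a legitimate design choice. But the plan never says that it represents dependence and gives no cut-off for the frequency groups, so the two statements remain unreconciled.

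**Power figures.** They assume that dependence is the sole moderator and is measured without error, so a proxy must lose. This objection stands in full, as step 5 shows.

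**Scope.** Adding interactions for every outcome would multiply tests, while the hypothesis concerns puffing and exposure only. This stands and limits the fix.

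**Conclusion.** The concern holds in a limited form. As written, the secondary hypothesis on users with low dependence has no specified test on dependence, although the score needed for one is collected. This follows from the text and needs no numerical assumption.

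The fall from about 83% to between 10% and 35% is illustrative only. It rests on an assumed correlation of 0.37, assumed score–frequency correlations of 0.3 to 0.7, a median split, and dependence rather than frequency as the true moderator. The firmer numbers are the detectable correlations, 0.355 with 60 and 0.253 with 120. The pooled figure also assumes that the score has the same slope in both parts, which differ in product and in size of nicotine reduction.

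The change is worth making before analysis because it is cheap and lets the trial address a hypothesis it states.

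**What to change.** 1. In the mixed model, pre-specify the session-1 Penn State score (continuous) and its interaction with nicotine condition for puff topography and aldehyde emissions, as the test of the secondary hypothesis. The one-way ANOVA for Aim 3 has no place for this term, so the mixed model must be extended to emissions.
2. Because the hypothesis is of minimal compensation, report the estimated condition effect with its confidence interval at a stated low score, not only the interaction p-value.
3. Label any such interaction for craving, withdrawal or satisfaction as exploratory.
4. State that the Aim 1 dependence response means acute change on the urges and withdrawal scales, and list the Penn State index as a baseline moderator. Say in Table 2 that the session-1 value is used; the baseline-only asterisk is attached only to demographics.

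If the sponsor means frequency, the alternative is to reword the Background hypothesis, define the frequency groups and put frequency × condition in the model.

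**Cost.** No new data; wording and a few extra interaction tests with modest power. Four topography measures and 14 aldehydes would give 4 + 14 = 18 tests per part. Naming one lead topography measure and one lead emission measure keeps the number small.

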## **Study Aims**

Aim 1. To assess the subjective and clinical effects of NR on ENDS users. Participants will undergo 2 ENDS use sessions that are preceded by 12-hour abstinence, with session order counter-balanced to mitigate order and carry-over effects. This study will focus on pre-post-use assessment of craving, withdrawal, satisfaction, intention to quit or use in the future, lung functions (e.g. FEV1 % predicted; FEV1/FVC, CO diffusing capacity-DLCO), and symptoms (e.g. dry mouth, eye irritation, palpitation, nausea). This aim will show ENDS users' response to NR on product satisfaction, dependence, lung functions and symptoms.

Aim 2. To assess puffing behavior in response to NR. Under the same protocol, puff topography (e.g. puff volume, puff frequency, duration) will be assessed continuously during the 2 sessions, while plasma nicotine will be measured pre-post sessions to assess nicotine boost and its correlation to puffing parameters. This aim will help understand users' compensatory puffing in response to NR and its effect on plasma nicotine.

Aim 3. To assess exposure to toxicants associated with NR. We will measure toxicant emissions (14 aldehydes) in the analytical lab using a smoking robot that reproduces the puff-by-puff behavior (playback) of each participant for all two nicotine conditions (Aims 1, 2). This aim will reveal how compensatory puffing behavior in response to NR influences acute exposure to pulmonary toxicants.

The proposed studies will give clear evidence on the potential of NR regulations to limit the addictiveness and use of ENDS, and to help predict any potential side effects of NR on ENDS users.

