Screening, and informed consent: Individuals who are identified as potentially eligible based on the phone screening will be asked to attend an onsite-screening, which will involve assessment of inclusion/exclusion criteria, physical examination, COVID-19 screening, and urine pregnancy testing for women. Prior to screening, potential participants will undergo a review of the study and consent procedures to ensure that they understand the study, its risks/benefits, and their rights as research participants. Consented (written) individuals will then undergo a physical examination conducted by the research nurse, who will have access to an on-call Medical Monitor (physician) in case of concern or for consultation at any point of the study as it is the standard practice in our lab. Successfully consented participants will be scheduled for their 1st session and asked to abstain from all tobacco/nicotine use 12 hours prior to it.

Sample size. All power calculations were performed with PASS19 (PASS, 2019). We built our calculation of the sample size for this study based on our preliminary study of the effect of NR on subjective (e.g. craving, urges) and puff topography measures (pls. see Preliminary Studies), where medium effect size (Cohen's  $f=0.2$ ) depending on nicotine condition was detected. Expecting a maximum 20% loss due to noncompliance with abstinence or study protocol (Vargas-Rivera et al., 2020), this study will include a dropout inflated sample of 150 ENDS users. Using repeated measures ANOVA F-test with 2 within and 1 between factors, a total dropout adjusted sample size of 120 (2X60) participants will have at least 80% power to detect small to medium-size effect (Cohen's  $f=0.1-0.2$ ) or larger for 2 within-subject (NR condition and time) and 1 between subject (use frequency) factors, as well as their interactions at 0.05 level of significance, assuming sphericity and a moderate correlation (0.5) among repeated measures (Cohen, 1988).

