## **AIM 3: To assess exposure to toxicants associated with nicotine reduction.**

**Objective and hypothesis:** This aim will help elucidate how compensatory puffing behavior in response to NR affects exposure to pulmonary toxicants. *We hypothesize that partial but not total NR will be associated with compensatory puffing behavior that will, in turn, lead to greater exposure to toxicants.*

**Analytical methods.** The analytical assessments will be conducted at the AUB Aerosol Research Laboratory (ARL). The ARL is equipped with two digital playback smoking machines necessary for Aim 3. These two machines, developed and tested by our team at AUB, are to our knowledge unique to this setting and are not available in any other laboratory. The proposed work in Aim 3 is built on the ARL framework and infrastructure for aerosol generation, sampling, and chemical analysis.

**Aerosol generation and sampling:** The deidentified puff topography data will be shared via Microsoft Sharepoint between FIU and AUB Aerosol Lab, thus, all communication will be encrypted between client and server using SSL 2048 bit keys. Access to the lab and data will be granted only by permission of Drs. [name] (PI), and [name] (local PI at AUB).

Once the puff topography files have been received by the ARL, we will use ALVIN (Aerosol Lab Vaping Instrument) (Talih et al., 2015, 2017) to draw aerosols from the ENDS devices, for each of the 240 topography sessions. For each session, ALVIN will be programmed to reproduce the puff topography data generated in the clinical lab. The generated aerosol will be drawn through a Gelman type A/E 47mm glass fiber filter followed by a 2,4-dinitrophenylhydrazine-coated silica cartridge (type LpDNPH H10) cartridge, for nicotine and aldehydes quantification, respectively (see Talih et al., 2015, 2017; El-Hellani et al., 2018 for more detail). The pods (e.g. JUUL) and batteries will be shipped from the same batch as those used at FIU to minimize biases. A new pod will be used for every session. Each pod will be pre-conditioned before sampling by drawing 15 4-second puffs at 1 LPM using ALVIN. We will use a quality assurance protocol and ENDS electrical performance tester developed at the ARL to ensure that each battery and pod are within tolerance (Talih et al., 2019, 2020b).

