mentioned covariates. Given the known sex-related differences in nicotine dependence (Benowitz et al., 2006), to assess if sex has any effect on the results, it will be considered as a covariate and we will test the pre-planned interaction with it to determine the heterogeneity of the study outcomes by sex as well as potential differential effects. Similarly, for categorical outcomes we will apply generalized linear models and estimating equations with the same main effects as described above, modeling within factors as random effects. We will test for the carry-over effect statistically and will control for it when testing for the primary factors (Senn, 2002).

For Aim 3, we will use a one-way ANOVA to test the effect of NR on aldehyde emissions and multiple linear regression analysis to assess the influence of puff topography data (puff volume, duration, number, and interpuff interval) on aldehyde emissions. Additionally, we will measure the relation between the plasma nicotine levels obtained in the clinical lab and measured nicotine yields obtained in the analytical lab using linear regression. Significance levels will be adjusted for violations of the sphericity assumption using Huynh-Feldt corrections (Keppel, 1991). All differences will be considered significant at the alpha level of 0.05 using adjusted p-values where appropriate. Due to the nature of laboratory data collection, missing data is rare and it usually occurs due to instrument malfunction. All data are collected and checked for completeness by laboratory staff. In the case of missing data, which we expect to be minimal, we will use a regression model based on multiple imputations with all available outcome data, demographic, and clinical variables as predictors. This will be carried out in 25 random repetitions under missing at random assumption, analyzed using methods described above and results will be combined to produce unbiased overall estimates and standard errors of the experimental conditions. As a sensitivity analysis completers results will be compared with multiple imputation results.

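### Aim 3 hypothesises that nicotine reduction raises aldehyde exposure through compensatory puffing, but no planned analysis says how much of an aldehyde difference comes from puffing rather than from the liquid

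*Combined protocol and SAP*

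**What the plan says.** Aim 3 is framed as a mechanism in two places. Study Aims: "This aim will reveal how compensatory puffing behavior in response to NR influences acute exposure to pulmonary toxicants". The hypothesis in the AIM 3 section is that "partial but not total NR will be associated with compensatory puffing behavior that will, in turn, lead to greater exposure to toxicants".

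The data come from machine playback, described under aerosol generation in the AIM 3 section. Aerosol is drawn "for each of the 240 topography sessions". "For each session, ALVIN will be programmed to reproduce the puff topography data generated in the clinical lab", and "A new pod will be used for every session". Pods are "shipped from the same batch as those used at FIU to minimize biases". No run is described in which two strengths share a puff profile, or in which puffing from one condition is replayed on the other condition's pod. Each pod receives a fixed set of conditioning puffs, but these come before sampling.

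For Aim 3, the Statistical analysis section says "we will use a one-way ANOVA to test the effect of NR on aldehyde emissions". Separately, it plans a multiple linear regression of emissions on four topography summaries: volume, duration, count and interval between puffs. Nicotine condition is not named among the predictors. No mediation analysis or other decomposition is mentioned.

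Two other sections matter here. Study Design splits the trial into an NJOY part (5% and 3%) and an SREC part (5% and 0%). Aim 2 measures topography in both sessions of every participant.

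**The concern.** The hypothesis has two links: NR changes puffing, and the changed puffing raises aldehyde exposure. Between a participant's two sessions, both the puffing and the liquid differ. An aldehyde difference between conditions is therefore the sum of a puffing part and a liquid part.

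The ANOVA estimates that sum. The regression asks whether sessions with more puffing emit more, which can be true whatever NR does. Reported side by side, the two results do not say what share of the NR difference came from puffing. If both parts move, a pattern of higher exposure under partial but not total NR could be partly a property of the liquids and still be reported as user compensation. If they move in opposite directions, a real contribution from puffing could be hidden in a small total.

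**Working it through.** **1. Number of playback runs.** The sample size paragraph under Participants and recruitment says "a total dropout adjusted sample size of 120 (2X60) participants will have at least 80% power", and each participant attends two sessions. 120 × 2 = 240, which matches the plan's figure. With one replay per session, the count leaves no runs for a crossed or common-profile set. That is an inference from the count; the plan does not say it in words.

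**2. What each analysis estimates.** Let L = 1 for the reduced-nicotine session and 0 for 5%, T a topography summary and Y log aldehyde yield:

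- T = participant level + c·L + error
- Y = b·T + g·L + error

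Here c is the change in puffing, b the effect of puffing on emissions, and g the liquid effect at equal puffing.

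- Total NR effect = b·c + g. The planned ANOVA estimates this.
- Aim 2 estimates c.
- The planned regression, without L, estimates b + g·cov(T, L)/var(T).
- A regression with both T and L estimates b and g, so the puffing component is the total minus g.

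**3. Range under assumed values.** The documents give no emissions per ml by strength. As an assumption, let emissions per ml change by −15%, 0 or +15%. The ratio of total yield to the 5% condition is then:

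| Puffed volume | Liquid −15% | Liquid 0 | Liquid +15% |
|---|---|---|---|
| unchanged | 0.85 | 1.00 | 1.15 |
| +15% | 1.15 × 0.85 = 0.98 | 1.15 | 1.15 × 1.15 = 1.32 |

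A ratio of 1.15 arises from puffing alone or from liquid alone, and the total does not distinguish them.

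**4. Simulation.** All effect sizes and variances are assumptions: 60 participants in a part, two sessions each, b = 1.0, topography SD 0.7 between and 0.5 within participants, residual SD 0.5, 2000 replicates.

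| c | g | Mean difference | ANOVA rejects | Slope, no condition | Slope, with condition | Condition coefficient |
|---|---|---|---|---|---|---|
| 0.5 | 0 | 0.494 | 85.2% | 1.000 | 1.001 | −0.001 |
| 0.25 | 0.25 | 0.501 | 86.1% | 1.021 | 1.000 | 0.249 |
| 0 | 0.5 | 0.496 | 85.4% | 0.999 | 0.999 | 0.498 |
| 0.5 | −0.5 | −0.001 | 0.8% | 0.920 | 1.002 | −0.504 |
| 0 | 0 | −0.001 | 0.8% | 0.999 | 0.999 | −0.002 |

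The ANOVA gives the same answer in the first three rows. The slope without condition was significant in every run of every row, including the two with no compensation. The 0.8% lies below the nominal 5% because a one-way ANOVA ignores the pairing of sessions.

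The formula in step 2 reproduces the slope in row four: cov = 0.5 × 0.25 = 0.125; var = 0.49 + 0.25 + 0.25 × 0.25 = 0.8025; 1 − 0.5 × 0.125/0.8025 = 0.92.

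**5. Recovering the split.** Total minus condition coefficient gives 0.495, 0.252, −0.002 and 0.503 in the first four rows, against true puffing components of 0.5, 0.25, 0 and 0.5. These use only own-pod replays. The check used ordinary regression, and its data were generated linear and without interaction, so it shows that the split can be identified under those conditions, not that they hold here.

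**The case against.** The strongest reply is that the plan already guards against the worst misreading. A reader might infer that an aldehyde difference would be credited to compensation even if puffing had not changed. The documents do not support that: Aim 2 measures topography in both conditions, and the hypothesis requires compensatory puffing as well as greater exposure. Unchanged puffing would be visible in Aim 2, and so would increased puffing masked by an offsetting liquid effect.

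A reader might also infer that replaying each session on its own pod is the flaw and makes separation impossible. It is not. Own puffing on own liquid is the right contrast for total exposure, and step 5 shows that the same data allow the split by modelling.

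Third, one might infer that leaving condition out seriously distorts the topography slope. In the simulation it ran from 0.92 to 1.02 against a true 1.0, even with large assumed liquid effects, so this is minor.

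It is also fair to say that no passage suggests that aldehydes differ by strength at equal puffing, that the plan limits other product differences (one brand within a part, a shared batch, tolerance testing), and that a one-sentence model description may not list every covariate.

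All of this narrows the point without removing it. Aim 2 shows whether puffing moved, not how much of the aldehyde difference follows from it. Nothing in the plan states or tests equal emissions across strengths. If a condition term is intended, the section should say so.

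**Conclusion.** The point holds as a gap in the analysis, not as a design fault. The total effect of NR on emissions is validly estimable from the planned playback. Its attribution to compensatory puffing, which Study Aims and the AIM 3 hypothesis both claim, is not addressed by any planned analysis, because condition and topography are never listed in the same aldehyde model.

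The size of any liquid effect, and so of any misattribution, cannot be derived from the documents. The 15% figures and the simulation settings are illustrations. The conclusion that the ANOVA cannot apportion the difference does not depend on them, because the total is b·c + g for any values.

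**What to change.** In the Aim 3 paragraph of Statistical analysis, replace the two separate analyses with a session-level mixed model of aldehyde emissions, fitted within each product part (NJOY 5%/3%; SREC 5%/0%), with nicotine condition and a participant effect:

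1. Fit it without topography and report the condition effect as the total NR effect.
2. Fit it with topography, including total puffed volume (number × mean volume), and report the condition effect as the liquid effect at equal puffing.
3. Interpret the difference between the two, together with the Aim 2 puffing result, as the puffing component. State the assumptions: linearity, no condition-by-topography interaction (to be checked), and topography summaries that capture what drives emissions.

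This needs no new data or runs, only a revised model statement and an interpretation sentence. If the sponsor prefers not to do it, the Study Aims sentence and the AIM 3 hypothesis should be reworded to claim only the total effect of NR on emissions.

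As an optional check, a small set on the playback machine under one fixed puff profile would measure the liquid effect directly, though only at that profile. For example, 5 pods for each of the 4 product-strength combinations is 20 runs, or 20/240 = 8.3% more. The main fix does not depend on it.
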